3 STUDY OBJECTIVES.....	7
4 STUDY DESIGN	7
4.1.1 Efficacy endpoints	7
4.1.2 Safety Endpoint	7
4.2 Study Duration.....	8
4.3 Study Assessments	8
4.3.1 Safety Assessments.....	8
4.4 Study Discontinuation	8
4.5 Investigator Selection.....	8
5 STUDY POPULATION	8
5.1 Study Subject Recruitment and Selection	8
5.1.1 Inclusion Criteria	9
5.1.2 Exclusion Criteria.....	9
5.2 Subject Numbering.....	10
5.3 Subject Discontinuation Criteria.....	10
6 STUDY PROCEDURES	10
6.1 Screening and Enrollment Visit Procedures	10
6.2 RF Treatment Visit	10
6.3 Biopsy Collection Visit	11
7 ADVERSE DEVICE EFFECTS.....	12
7.1 Definitions	12
7.1.1 Adverse Device Effect (ADE)	12
7.1.2 Serious Adverse Device Effect (SADE).....	12
7.1.3 Anticipated Serious Adverse Device Effect (ASADE).....	12
7.1.4 Unanticipated Serious Adverse Device Effect (USADE/UADE)	12
7.2 Recording Adverse Device Effects	14
7.3 Follow-up of Subjects after ADEs	14
8 POTENTIAL RISKS / BENEFITS	14
8.1 Potential Risks	14
8.2 Potential Benefits	15

8.3 Risk Management.....	15
9 DATA ANALYSIS PLAN.....	16
9.1 Sample Size.....	16
9.2 Analysis Sets	16
9.3 Analysis of Efficacy Endpoints	16
9.3.1 Primary Endpoint Analysis	16
9.4 Safety Analyses.....	16
10 SUBJECT PAYMENT.....	16
11 STUDY MANAGEMENT AND ADMINISTRATIVE PROCEDURES.....	16
11.1 Training and Monitoring.....	16
11.2 Informed Consent	17
11.3 Protocol Compliance.....	17
11.3.1 Protocol Amendments.....	17
11.3.2 Protocol Deviations.....	17
11.4 Study Personnel	18
11.5 Disclosure of Financial Interest.....	18
11.6 Data Collection, Record Keeping and Storage.....	18
11.7 Subject Confidentiality.....	19
11.8 Publication Policy.....	20
REFERENCES.....	21
Appendix 1: Study Schedule.....	23
Appendix 2: Pain Rating Scale	24
Appendix 3: Fitzpatrick Skin Type Classification	25
Appendix 4: Before and After Treatment Instructions	26

Protocol Summary

Title	Clinical Study to Evaluate the Performance the truSculpt Radiofrequency Device for Lipolysis of Abdominal Fat
Objective	To evaluate the truSculpt Radiofrequency Device for non-invasive fat reduction in abdominal tissue
Study Design	A single-center, prospective, non-randomized, open-label study
Enrollment	Approximately 14 subjects
Primary Endpoint	Histological evaluation of tissue for selective fat necrosis, with sparing of the dermis and epidermis, following truSculpt treatment vs. untreated contralateral control
Safety Endpoint	Incidence and severity of adverse device effects during the study period, including subject pain level during RF treatment
Subject Population	Female and male subjects, age 24 to 60 years, Fitzpatrick skin type I-VI
Planned Schedule	First subject enrolled: June 2017 Last subject last visit: June 2018

1 PURPOSE

The purpose of this investigation is to evaluate the performance of the truSculpt Radiofrequency Device for non-invasive lipolysis of abdominal fat.

2 BACKGROUND INFORMATION

Unwanted excess fat pockets/bulges have been among the top concerns expressed by patients in the aesthetic field. Although surgical interventions produce the most definitive results with body contouring, these invasive methods require significant recovery time and come with inherent risks.

As a non-invasive option, laser, intense pulsed light (IPL), RF, or a combination of these technologies have been developed to reduce cellulite and body circumference with minimal recovery time and risks [1]. The tightening effect of the thermal energy generated by these devices has been used for reduction in cellulite and body circumference in areas including but not limited to arms, abdomen, thigh, back and flanks [2-14]. Although lasers and IPLs can target the deep dermal layers, the thermal effects of these devices are limited due to light scattering and energy absorption by water in the dermis.

RF, which is the most studied device in the non-ablative category, uses electrical current rather than light energy. Unlike light energy, radio waves can penetrate deeper depending on the frequency of operation. RF can be used with all Fitzpatrick skin types without jeopardizing epidermal integrity [15].

[REDACTED]

[REDACTED]

[REDACTED]

[REDACTED]

Sample labeling and directions for use can be found in the Operator's Manual for this device.

Table 1. truSculpt RF Device Specifications	
RF Power	[REDACTED]
Pulse Duration	[REDACTED]
Frequency	[REDACTED]
Target Skin Temperature	[REDACTED]
Handpiece Size	[REDACTED]

3 STUDY OBJECTIVES

The objective of this study is to evaluate the truSculpt Radiofrequency Device for non-invasive fat reduction in abdominal tissue.

4 STUDY DESIGN

This is a single-center, prospective, non-randomized, open-labeled study in approximately 14 subjects, age 24 to 60 years, who are scheduled for abdominoplasty, and will undergo one RF treatment in the abdominal region. Subjects will receive 1 RF treatment with the truSculpt device [REDACTED]

[REDACTED]

One treatment will be performed by the truSculpt device on one abdominal subarea, while the other abdominal subarea will not be treated and will serve as a control. Subjects will have incisional or full-thickness punch skin biopsies. Biopsies will be harvested from tissue to be removed during the abdominoplasty, and will subsequently be cultured. At least two biopsy samples for each subject will be obtained during the abdominoplasty: at least one from the treatment area and at least one from the control area. The purpose of the biopsies is to examine and compare potential histological changes in cutaneous and sub-cutaneous tissue levels that occur as a result of RF treatment.

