6.1 Screening and Enrollment Visit Procedures

The following screening procedures will be performed:

1. Informed Consent process.
2. Review of subject medical history.
3. Assessment of treatment area.
4. Assessment of concomitant medications.
5. Assign subject to a subgroup.

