6.2 RF Treatment Visit

The following procedures will be performed at the RF Treatment Visit:

1. If needed, cleanse subject's treatment area with a mild cleanser to remove any cosmetics, perfume or lotions and then dry the area.
2. Prior to performing RF treatment, the Investigator should confirm the subject continues to meet the study eligibility criteria, including asking about any changes in medical history and/or concomitant medications or significant increase or decrease in subject weight.
3. Using a surgical marker, mark the subject's abdomen as it will be marked on the day of the subsequent planned abdominoplasty procedure.

4. Place the return pad on the subject's upper lateral back. Connect the neutral electrode cable after the return pad has been applied.
5. The subject should be lying down and comfortable while undergoing RF treatment and the operator should have easy access to the treatment area.
6. Conduct RF treatment according to the parameters listed in Table 2 with one imprint applied to the subject's abdomen over the tissue intended to be removed during the following abdominoplasty procedure.

Table 2. TruSculpt RF Device Treatment	
RF Power	[REDACTED]
Pulse Duration	[REDACTED]
Frequency	[REDACTED]
Target Skin Temperature	[REDACTED]
Handpiece Size	[REDACTED]

7. Place the handpiece on the skin of the area to be treated and ensure the electrode is in full contact with the skin at all times. Do not apply excess pressure as this may diminish treatment effects and cause additional subject discomfort. The operator must wear surgical gloves during RF treatment.
8. After the imprint is delivered, an image will be taken of the subject's markings and post-treatment hyperemia pattern showing the location of the imprint. The image will be added to the subject's chart. The pulse duration for the imprint and the target temperature achieved during RF treatment will be recorded in the subject's chart.
9. The subject will be asked to rate the average level of discomfort experienced during and after completion of treatment using the Pain Rating Scale found in Appendix 3.
10. Investigator will assess and record any immediate post-treatment adverse device effects.
11. The "Before and After Treatment Instructions" will be explained and provided to the subject (see Appendix 4).

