6.3 Biopsy Collection Visit

The Biopsy Collection visit will occur on the same day as the abdominoplasty surgery. The following procedures will be performed prior to and during abdominoplasty surgery:

1. Review of subject medical history.
2. Assess and record any additions, changes and/or deletions in prescription and nonprescription concomitant medications since the previous study visit.
3. Record severity and duration of any adverse device effects following RF treatment and assess for any new adverse device effects.
4. Biopsy collection procedure:
 - a. Refer to the patient chart and identify the RF treatment location.
 - b. During the biopsy collection procedure, at least one skin biopsy (approximately 10 mm x 10 mm; full thickness) will be taken from the area treated with RF; and at least one skin biopsy (approximately 10 mm x 10 mm; full thickness) will be taken from an equivalent contralateral non-treated area as a control.

c. Each biopsy sample will be immediately placed in the prepared fixative vials, making sure the samples are fully submerged in the solution. The vials will be labeled with the subject ID number, subject initials and biopsy date. The vials will be randomly numbered, and the numbers of the vials containing the biopsy from the RF treated and control skin will be recorded in the patient chart. The histologist will remain blinded to the nature of each biopsy sample (treatment or control).

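### The readable text gives no rule for choosing which abdominal side receives RF, so operator choice of side could tilt the descriptive treated-versus-control contrast

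*Combined protocol and SAP*

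**What the plan says.** **Design.** Section 4 reads: "This is a single-center, prospective, non-randomized, open-labeled study in approximately 14 subjects". The Protocol Summary also labels the study non-randomized and open-label. Section 4 continues: "One treatment will be performed by the truSculpt device on one abdominal subarea, while the other abdominal subarea will not be treated"; the untreated subarea is the control. Text just before that sentence is redacted.

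**Endpoint.** The primary endpoint is histological: selective fat necrosis, with dermis and epidermis spared, against the untreated side (contralateral in the Protocol Summary, bilateral in 4.1.1.1).

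**Screening.** The last step in 6.1 is "Assign subject to a subgroup". No readable text defines the subgroup.

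**Treatment.** In 6.2, step 3 marks the abdomen as for surgery. Step 6 delivers RF "with one imprint applied to the subject's abdomen over the tissue intended to be removed during the following abdominoplasty procedure". Step 8 photographs the markings and the imprint location afterwards. Apart from the device settings in Table 2, these steps are readable, and none assigns a side.

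**Biopsy.** Section 6.3, step 4b, takes the second sample "from an equivalent contralateral non-treated area as a control". Step 4c adds: "The vials will be randomly numbered, and the numbers of the vials containing the biopsy from the RF treated and control skin will be recorded". The same step keeps the histologist blind to sample type.

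**Analysis.** Section 9.3.1 plans no formal test, only a descriptive summary by area, with no adjustment for side or baseline. Section 9.1 bases the sample size on clinical judgement.

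**The concern.** In a within-subject design, the comparison is only as good as the match between the two sites. The subject's own abdomen removes differences between subjects, but differences between the two sides of one abdomen remain. If an unblinded operator picks the side, the choice can follow something visible, such as skin quality, an old scar or apparent fat thickness, or simply habit.

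Two things are at stake:

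- **Background reading.** If untreated tissue would read differently on the two sides, for necrosis or for dermal and epidermal condition, that difference is added to the contrast.
- **Suitability of the site.** If the chosen side suits the device better, the result describes favourable sites rather than the abdomen generally. This does not create a false effect, but it limits what the result represents.

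Neither can be removed afterwards. The visit procedures list no pre-treatment biopsy, and the analysis has no side or baseline term.

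**Working it through.** **1. Is there a side rule in the readable text?** Following the choice through the study:

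| Stage | Where | What it does about side |
|---|---|---|
| Design | Section 4 | One subarea treated, the other not; which one is not stated |
| Screening | 6.1, step 5 | Assigns an undefined subgroup |
| Marking | 6.2, step 3 | Surgical outline only |
| Imprint | 6.2, step 6 | Over tissue to be removed; no side given |
| Photograph, CRF drawing | 6.2, step 8; 11.6 | Record the location once chosen |
| Control site | 6.3, step 4b | Follows from where the imprint went |
| Random vial numbers, blinded histology | 6.3, step 4c | Act after both sites are fixed |
| Analysis | 9.3.1 | No side or baseline term |

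The only random element is the vial number. It protects the assessment, not the selection of the side.

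**2. Is there a planned figure to reproduce?** No. The plan gives no alpha, power, effect size or SD, so no stated figure bears on this point.

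**3. Illustration of size.** This covers the background-reading route only, on assumptions that are not in the documents. Let the untreated left-right difference in a continuous histology score be Normal with mean 0 and SD sigma_d, with n = 14 and no device effect. The operator treats the side with the higher untreated reading with probability q.

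The mean absolute difference is sqrt(2/pi) × sigma_d = 0.798 sigma_d, so

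expected shift in treated minus control = (2q − 1) × 0.798 sigma_d.

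| q | Arithmetic | Expected shift | Simulated mean (200,000 runs) |
|---|---|---|---|
| 0.5 (random side) | 0 × 0.798 | 0 | 0.001 |
| 0.6 | 0.2 × 0.798 | 0.16 sigma_d | 0.160 |
| 0.75 | 0.5 × 0.798 | 0.40 sigma_d | 0.398 |
| 1.0 | 1.0 × 0.798 | 0.80 sigma_d | 0.797 |

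Under random assignment the chance SD of the mean is sigma_d / sqrt(14) = 0.27 sigma_d (simulated 0.266). At q = 0.75 the expected shift is therefore about 0.40 / 0.27 = 1.5 chance SDs.

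**4. Habit rather than selection.** Suppose instead that left exceeds right by a constant m on average. With k of 14 subjects treated on the left, the contribution to the contrast is m × (2k − 14) / 14. At k = 14 this is m; at k = 7 it is 0. It matters only if m differs from zero, and the documents give no value for m.

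**The case against.** **A rule may exist out of sight.** A reader might infer that the protocol has no side rule at all. The documents do not support that: text in section 4 is redacted, the subgroup in 6.1 is unexplained, and the Appendix 1 schedule is not shown. The claim is therefore limited to readable text. Still, 6.2, where an operator would apply a rule, is readable apart from the settings and contains none. The non-randomized label also makes a hidden random assignment unlikely.

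**The imprint could sit on the midline.** A reader might infer from step 6 of 6.2 that a central imprint is allowed, leaving no valid control. Section 4 requires a second, untreated subarea and 6.3 requires a contralateral counterpart, so an off-midline imprint is already implied. Explicit wording would only clarify this.

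**A side difference is not automatically a device effect.** This stands. Thicker fat is not necrosis, and treating one side throughout does harm only if the sides differ systematically in what the histologist reads. Section 5.1.2 also narrows the field. It excludes earlier invasive cosmetic surgery and recent cosmetic treatment to the area, keloid or hypertrophic scarring, and infection, dermatitis, rash or other skin abnormality there. Ordinary scars from non-cosmetic surgery are not named, and 5.1.1 does not ask for symmetry.

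**No test is planned and the study is openly non-randomized.** Also true, so no type I error rate is at stake. But a descriptive contrast in about 14 subjects relies heavily on comparable sites, and the label does not prevent assigning the side within each subject.

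**Location is already recorded.** An imbalance in side could be seen afterwards. The reason for the choice, and the spot not chosen, could not.

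**Conclusion.** The point holds as a cheap improvement to the design. In the readable text the operator may choose the treated side, and the existing safeguards act too late to control that choice. All of the roughly 14 pairs are exposed, but exposure is not bias. The documents give neither the left-right variation nor the strength of any preference. The 0.16 to 0.80 sigma_d range rests entirely on an assumed continuous Normal score and an assumed q. If untreated fat shows almost no necrosis, which the documents do not state, the effect on the necrosis component would be small. The dermal and epidermal sparing component could still be affected by choosing the better-looking skin. A reader might go further and infer that the contrast is confounded, or that any observed necrosis could reflect choice of side. Nothing in the documents shows a side difference in the endpoint, so neither conclusion follows.

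**What to change.** 1. **Section 6.1:** check at screening that both sides offer a suitable spot, because assignment will come after enrolment.
2. **Section 6.2, after step 3 and before step 6:** mark two mirror-image candidate spots, one on each side of the midline, within the tissue to be removed. Only then open the next entry of a pre-generated, randomly ordered left/right list in small balanced blocks. Small blocks suit a sample size stated as approximate; a fixed list of 7 left and 7 right balances only if exactly 14 are treated.
3. **CRF:** record the assigned side and the treated side, and log any departure with its reason.
4. **Section 9.3.1:** report treated side for each subject beside the histology result.
5. **Protocol Summary and section 4:** amend the non-randomized wording to say that the treated side is randomised within subject.
6. If redacted text or the subgroup step already holds a side rule, reconcile it with 6.2 and state it there.

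**Cost:** a list of about 14 lines, a CRF entry for assigned and treated side, and short wording changes in several places. No visit or procedure is added, and no device setting changes. The main downside is an occasional subject with only one suitable side, found at screening or logged as a departure.

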4.1 Study Endpoints

4.1.1 Efficacy endpoints

4.1.1.1 Primary Efficacy Endpoint

- Histological evaluation of tissue for selective fat necrosis, with sparing of the dermis and epidermis, following truSculpt treatment vs. untreated bilateral control.

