5.1.1 Inclusion Criteria

To be included in the study, subjects must meet all of the following Inclusion Criteria:

1.	Male or Female, 24 to 60 years of age (inclusive)
2.	Fitzpatrick Skin Type I – VI (Appendix 3)
3.	Has visible fat bulges or skin laxity in the abdominal region
4.	Scheduled to undergo surgery (abdominoplasty).
5.	Non-smoking for at least 6 months and willing to refrain from smoking for the duration of the study.
6.	Subject must agree to not undergo any other procedure(s) in the abdominal region during the study period.
7.	Subject must be able to read, understand and sign the Informed Consent Form.
8.	Subject must adhere to the follow-up schedule and study instructions.
9.	Subject must adhere to the same diet/ exercise/medication regimen for the entire course of the study.
10.	Willing to provide histology samples during the surgery from the intended to be harvested areas.
11.	Post-menopausal or surgically sterilized, or using a medically acceptable form of birth control at least 3 months prior to enrollment and during the entire course of the study, and no plans to become pregnant.

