11.6 Data Collection, Record Keeping and Storage

The principal investigator is responsible for assuring that all study records including case report forms (CRFs), informed consent forms, device accountability records, source documents (e.g., medical records, histology reports etc.) and other study records are complete, accurate and recorded in a timely manner.

CRFs should not be the only record of a patient's participation in the study and will be used for transcribing data from source documents which are the point of first entry of data collected for each subject (with the exception of documents listed under **B**). The investigator or research staff at the site will ensure that:

A. Source documentation thoroughly and adequately documents:

1. That patient is participating in a clinical study and has been properly informed and consented prior to participation in the study,
2. Medical history,
3. Concomitant medications,
4. Patient's condition upon entering and during the course of the study,
5. Any adverse event(s) that might have occurred (in addition to the Visit CRFs and/or Adverse Device Effect CRF and/or Cutera SADE form completed),
6. Results of any diagnostic tests/histology conducted during the study.

B. The following data will be recorded directly onto CRFs:

7. Patient meets study inclusion and exclusion criteria,
8. A record of the treatment parameters, including the date of each RF treatment and any other adjunct therapy, a drawing of the patients abdomen showing the treatment location, and the vial numbers containing control and treatment biopsies,
9. Any protocol deviations,
10. Subject Questionnaire(s),
11. Study related improvement assessments by the investigator or investigator's designee,

12. Treatment-related pain ratings.

C. The following documents will be maintained in the study records:

13. The Investigator or the research staff will check signed informed consent for accuracy and will always keep the original copy of the signed informed consent in the CRF binder.
14. All correspondence with an Institutional Review Board (IRB), the sponsor, or FDA including required reports will also be retained in the study records.
15. Records of receipt, use or disposition of the investigational device.

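### Does the statement in Section 4 that the biopsies will be cultured put the histological primary endpoint in doubt, when Section 6.3 fixes every sample?

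*Combined protocol and SAP*

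**What the plan says.** Section 4 (Study Design) describes the biopsies in one short paragraph. It says "Biopsies will be harvested from tissue to be removed during the abdominoplasty, and will subsequently be cultured". The next sentence sets the minimum number: "At least two biopsy samples for each subject will be obtained during the abdominoplasty", with at least one from the treated area and one from the control area. The sentence after that gives the reason for taking them: "The purpose of the biopsies is to examine and compare potential histological changes in cutaneous and sub-cutaneous tissue levels".

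Section 6.3, step 4c, is the working instruction for the day of surgery: "Each biopsy sample will be immediately placed in the prepared fixative vials, making sure the samples are fully submerged in the solution". It goes on to cover labelling, random numbering of the vials, recording in the chart which numbers are treated and which control, and blinding of the histologist.

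The endpoint that these samples serve is in Section 4.1.1.1: "Histological evaluation of tissue for selective fat necrosis, with sparing of the dermis and epidermis", compared with untreated tissue from the same subject. Inclusion criterion 10 in Section 5.1.1 reads "Willing to provide histology samples during the surgery from the intended to be harvested areas". Section 11.6 lists, among the source records, "Results of any diagnostic tests/histology conducted during the study".

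**The concern.** Culture needs living tissue, and immersion in fixative ends viability. Read literally, the two sections give incompatible instructions for the same specimens.

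This would be serious if it were a real choice. The trial has one efficacy endpoint, read entirely from these biopsies. Each is taken on a single occasion, from tissue that is removed in the operation, so a mishandled specimen cannot be replaced. If a subject's samples were cultured and not fixed, there would be no sections in which to look for fat necrosis or for sparing of the dermis and epidermis. Section 9.2 rules out imputation, so that subject would contribute nothing to the primary summary.

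There is a second, smaller worry: the design section tells an IRB or a monitor that subjects' tissue will be put to a use that no visible procedure carries out.

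**Working it through.** No figure in the plan depends on this point, so there is nothing to recompute. The check is to compare the texts and ask what each reading would do to the trial.

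| Place | What it implies for the samples |
|---|---|
| Section 4, sentence on harvesting | Culture after removal |
| Section 4, sentence on purpose | Histological comparison of treated and control tissue |
| Section 4.1.1.1 | Histological primary endpoint |
| Section 6.3, step 4c | Immediate fixation of each sample, blinded histology |
| Sections 9.3.1 and 9.4 | Descriptive summary of the primary endpoint and of safety; no culture result |

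**Step 1. Can both statements hold for one sample?** No. A sample that goes at once into fixative is not available for culture.

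**Step 2. Can they hold for different samples?** The minimum of one biopsy per area leaves room for extras, so one might suppose that the spare ones are cultured. The wording does not support this. Step 4c covers each sample, and the Section 4 sentence covers the biopsies without restriction. Neither sets a subset aside. The conflict therefore stands on the visible text.

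**Step 3. Which statement directs the work?** Section 6.3 is a numbered procedure that names the container, the immersion, the labels, the vial numbers and the blinding. The culture clause sits in an overview and names no medium, laboratory, duration or measurement. Staff could carry out the first from the protocol alone. They could not carry out the second.

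**Step 4. What does each reading do to the result?**

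- *Section 6.3 is followed.* Every sample is fixed and read blind. The endpoint and its descriptive summary are as planned.
- *Extra samples are cultured in addition.* At least one fixed sample per area is still required, so the primary endpoint is still obtained. No reported analysis uses the culture.
- *All samples are cultured.* The endpoint is lost. For this to happen, staff at a single center would have to leave the prepared vials unused, skip the numbering and blinding steps, and devise a culture method that the visible protocol does not contain, in a study whose stated purpose is histology.

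Only the third reading does harm, and every other element of the plan points away from it.

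**Step 5. Could the clash change who is analysed?** No. Section 9.2 defines the efficacy set by completing the RF session and the safety set by starting it. How a specimen is handled does not enter either definition, so a deviation logged on this account would not remove a subject from either set.

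**The case for a change.** The strongest case for acting is this. Section 11.3 obliges the investigator to comply with all of the protocol's terms, and for biopsy handling that is impossible as written. Section 11.3.2 counts incorrect procedures as deviations. The clause covers every specimen: at least 2 per subject, so 2 × 14 = 28 if about 14 subjects enrol. Criterion 10 asks subjects only for histology samples, so culture would go beyond it. The repair is one clause and costs almost nothing.

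The wording clash stands, and so does the point that two sections on the same specimens ought to agree. The rest carries less weight.

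- *Compliance.* A monitor would check the biopsy visit against Section 6.3, where the steps are written, and would find that it had been followed.
- *The count of 28.* This shows how many specimens the clause mentions, not how many would be affected. It is not a firm floor either, because Section 9.1 plans for up to approximately 14 subjects. If Section 6.3 is followed, the number affected is zero.
- *Criterion 10.* It is an eligibility item about willingness to give samples. Nothing in the document makes it a definition of the permitted uses of tissue. The consent form is not in the public document, so nothing can be inferred about it.
- *Cost.* Section 11.3.1 requires both parties' signatures and IRB approval for an amendment. That is modest, but there is no gain in conduct or analysis to set against it.

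One could also ask for a rule on specimens that contain no evaluable fat. That is a separate matter from the word in Section 4. A blinded histologist would note such a specimen in the ordinary course, and the no-imputation rule in Section 9.2 already tells the analyst to treat the reading as missing.

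**Conclusion.** The inconsistency is genuine but clerical, and no change to the plan follows. Its effect on procedures, on the primary endpoint, on the analysis sets and on the descriptive summary is nil, provided that the site follows the stepwise instruction in Section 6.3. A single center with prepared fixative vials and a histological endpoint has every reason to do so. If the protocol is opened for some other reason, the word can be tidied then; it does not justify an amendment of its own.

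Two assumptions lie behind this. The first is that the redacted text before the quoted paragraph in Section 4, and the Appendix 1 schedule that is not shown, contain no culture step that replaces fixation. If they added culture of extra samples, the required fixed samples would still supply the endpoint. The second is that the word is a drafting slip. That is an inference from everything around it, not something the documents state. Confidence is high that the two sentences clash and that nothing in the visible plan depends on the clash, and somewhat lower about how the word came to be there.
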